8.1 Dose Modification

Individual drugs can be dose reduced as per the table below depending on the adverse event attribution. The dose reductions outlined in table 8.11 should first generally apply to AraC. If, however, the AE is clearly due to AZD1775, then AZD1775 can be reduced first as indicated in Table 8.11. After cycle 2, these modifications should be regarded as guidelines to produce mild-to-moderate, but not debilitating, side effects. If multiple adverse events are seen, administer dose based on greatest reduction required for any single adverse event observed. The treating MD, in discussions with the principal investigator, may reduce dose of either AraC or AZD1775 or the length of treatment at his or her discretion if it is in the best interest of the patient.

Dose	AZD1775	Cytarabine (AraC)
	[reduce AZD1775 first if clearly attributed to AZD1775]	[generally reduce AraC first]
0*	200 mg PO daily days 1-5 & 8-12	20 mg SC twice daily days 1-5 & 8-12
-1	200 mg PO daily days 1-5 & 8-12 ¹	10 mg SC twice daily days 1-5 & 8-12
-2	100 mg PO daily days 1-5 & 8-12	10 mg SC twice daily days 1-5 & $8-12^2$

8.11 AZD1775 combined with AraC (Arms A and B)

*Starting dose.

¹If toxicity is clearly attributable to AZD1775, AZD1775 can be reduced to 100 mg PO daily (days 1-5, 8-12) with continued AraC 20 mg SC twice daily days 1-5, 8-12. ²AraC may be decreased to 10 mg or 20 mg SC once daily at physicians discretion based on myelosupression, tolerance and clinical benefit (see also dose modification section .

NOTE: intermediate dose levels of 150 mg PO daily days 1-5 & 8-12 may be explored as a dose level -1a, based on PK, PD and clinical efficacy parameters and evaluation.

8.12 AZD1775 single agent (Arm C)

Dose	AZD1775
0*	200 mg PO daily days 1-5, 8-12, 15-19, 22-26

	200 mg PO daily days 1-5, 8-12, 15-19
1.0**	or
-1a	further reduction to 200 mg PO daily days 1-5 & 8-
	12 as tolerated
	100 mg PO daily days 1-5, 8-12, 15-19, 22-26
-1b**	
	100 mg PO daily days 1-5 & 8-12
2	
-2	

*Presumed starting dose of Expansion Portion.

**If at dose -1a leukemia breakthrough is observed, dose modification level -1b can be explored if continuous treatment may bring clinical benefit.

Note: Further dose modifications can be made, i.e. 150 mg PO daily days 1-5, 8-12, 15-19.

The above dose modification tables consider the fact that at present it is not clear if dose (Cmax) or continuous (length of therapy, AUC, trough) dosing of AZD1775 will achieve better disease control, hence the dose modification scheme (i.e. compared to hydroxyurea experience and titration).

- 8.2 A new course of treatment may begin on the scheduled Day 1 of a new cycle if:
 - AZD1775 or AraC related adverse event that may have occurred has resolved to \leq Grade 2 severity, except hematological adverse events for WBC, ANC, Platelets and Hemoglobin, or per table 8.3 guidelines.

If these conditions are not met on scheduled Day 1 of a new cycle, the subject will be evaluated as clinically indicated (i.e. weekly but at least every other week) and the new cycle of treatment will not be initiated until the adverse event has resolved as described above. Treatment can be continued on the drug that is not associated with the adverse event at the start of the following cycle and the drug associated with the adverse event may be reintroduced when the adverse event resolves to \leq Grade 1 if the treating physician feels that the patient will derive benefit from continued AraC or AZD1775 alone.

NOTE: If the patient experiences a significant adverse event requiring a dose reduction at the start of the next cycle, then the dose will remain lowered for that entire subsequent cycle. If that cycle is completed with no further adverse events >Grade 2, then the dose may be increased, at the investigator's discretion, one level at a time, in the following cycles.

8.3 Dose modification table for adverse events felt to be at least possibly related to AZD1775*** or AraC

→ → Use the NCI Common Terminology Criteria for Adverse Events (CTCAE) version 4.0* unless otherwise specified \leftarrow ←

CTCAE System/Organ/Class (SOC)	ADVERSE EVENT	AGENT	ACTION**					
BASED ON INTERVAL ADVERSE EVENT***								
Blood and Lymphatic System Disorders	Febrile neutropenia ≥ Grade 3	AZD1775	May omit dose until fever has resolved or returned to baseline. Dose to be restarted at same dose level. Treating physician may discuss possible dose reduction with one of the study chairs after the patient has completed 2 cycles. If clinical benefit is derived, AZD1775 may be continued if the infection is managed/controlled with appropriate medical intervention.					
Investigations	Neutrophil & Platelet count decrease \geq grade 4 NOTE: only applicable for patients with absolute neutrophil count (ANC) of \geq 1000mm³ and platelet count > 100,000/mm³ at baseline (i.e. MDS patients)	AZD1775	Omit dose until ANC and/or platelets have recovered to \leq grade 2. If clinical benefit is derived, AZD1775 may be continued if not recovered to \leq grade 2 after discussion of treating physician and study chair.					
Investigations	Creatinine increased Grade 2	AZD1775 AraC	 Omit dose until resolved to ≤ grade 1, then: If resolved in ≤ 7 days, then maintain dose level If resolved in > 7 days, then decrease by 1 dose level [If clinical benefit is derived, AZD1775 may be continued if the renal function is elevated but stable] Continue treatment at current dose level 					
	Creatinine increased Grade 3 and 4	AZD1775 AraC	Omit dose until resolved to \leq grade 1, then decrease dose by 1 dose levelOmit dose until resolved to \leq grade 1, then decrease dose by 1 dose level					
→ \rightarrow Use the NCI Common Terminology Criteria for Adverse Events (CTCAE) version 4.0* unless otherwise specified \leftarrow \leftarrow								
--	---	-------------------------	---	--	--	--	--	--
CTCAE System/Organ/Class (SOC)	ADVERSE EVENT	AGENT	ACTION**					
Investigations	Blood bilirubin increased ≥ Grade 3	AZD1775 AraC	 Omit dose until resolved to ≤ grade 1, then: If resolved in ≤ 7 days, then maintain dose level If resolved in > 7 days, then decrease by 1 dose level Continue treatment at next lower dose 					
	Blood bilirubin increased Grade 4	AZD1775 AraC	level Omit dose until resolved to ≤ grade 1, then decrease dose by 1 dose level Continue treatment at Dose level -1once					
	Alanine aminotransferase (ALT) increased and/or Aspartate aminotransferase (AST) increased Grade 3	AZD1775	 resolved to ≤ Grade 1 Omit dose until resolved to ≤ grade 1 or baseline then: If resolved in ≤ 7 days, then maintain dose level If resolved in > 7 days, then decrease dose by 1 dose level 					
	Alanine aminotransferase (ALT) increased and/or Aspartate aminotransferase (AST) increased Grade 4	AraC AZD1775 AraC	Continue treatment at next lower dose level Omit dose until resolved to ≤ grade 1 or baseline, then decrease dose by 1 dose level Continue treatment at Dose level -1					
Cardiac Disorders	Cardiac disorders – Other \geq Grade 4	AZD1775	Omit dose and discontinue patient from study					
Other Non- Hematologic events	≥ Grade 4	AZD1775	Omit drug and follow patient at least weekly or at least every other week until adverse event has resolved to grade ≤ 2 , restart drug at next lower dose level.					
AT TIME OF RETREATMENT								

otherwise specified ← ←								
CTCAE System/Organ/Class (SOC)	ADVERSE EVENT	AGENT	ACTION**					
Non Hematologic	All Non-Hematologic Toxicities Grade \geq 4 (With the exception of nausea, vomiting or diarrhea controlled with appropriate medications.)	AZD1775	Hold AZD1775 and AraC. Re-check patient at weekly or at least every other week. When event returns to ≤ grade 2, resume AZD1775 and AraC treatment at next lower dose level.					

 \rightarrow \rightarrow Use the NCI Common Terminology Criteria for Adverse Events (CTCAE) version 4.0* unless

Located at http://ctep.cancer.gov/protocolDevelopment/electronic_applications.ctc.htm

****** Use the following to describe actions in the Action column:

- > Omit = Treatment is not given for the day that is omitted, but treatment may resume once the adverse event has resolved as mandated in Table 8.2. For example, if treatment is omitted on Day 8, but the adverse event has resolved by Day 10, treatment may resume on Day 10 to complete the cycle. Missed doses will not be made up.
- ➤ Hold/Delay = Treatment can be made up as part of this cycle
- Discontinue = Treatment is totally stopped

***AraC can be continued each cycle regardless of dose hold or adjustments for AZD1775, if patient is presumed to derive clinical benefit from the intervention.

Patients whose treatment is interrupted or permanently discontinued due to an adverse event including abnormal laboratory values must be followed by their treating physician as clinically indicated. The maximum time allowed for treatment interruption due to toxicity is 6 weeks from the intended dosing day. If interruption is > 6 weeks, continuation of treatment is allowed on a case by case basis (i.e. clinical benefit) as determined by the treating physician. However, the patient will continue to be followed for toxicity. Dose interruptions should be reported on the appropriate Dosage Administration CRF.

9.0 **Ancillary Treatment/Supportive Care/Concomitant Medications**

- 9.1 Routine use of colony-stimulating factors (G-CSF or GM-CSF) is not recommended. Prophylactic use of colony-stimulating factors should be discussed with the study chair. Therapeutic use in patients with serious neutropenic complications may be considered at physician discretion. Recombinant erythropoietin to maintain adequate hemoglobin levels is discouraged and only allowed after discussion with the study chair.
- 9.2 Patients should receive full supportive care while on this study. This includes blood product support, antibiotic treatment and treatment of other newly diagnosed or concurrent medical conditions. All blood products and concomitant medications such as antidiarrheals, analgesics, anti-emetics received from the first administration of study drugs until 30 days after the final dose are to be recorded in the medical record. For more severe diarrhea (i.e. Grade 3 or 4) supportive measures such as hydration and antidiarrheals are recommended according to instutitional practice guidelines and as deemed appropriate by the medical situation (i.e. IV rehydration as in- or outpatient, antibiotics).
- 93 Anti-emetic therapy (excluding aprepitant) may be used in accordance with standard practice and/or the discretion of the investigator.

- 9.4 Hydroxyurea is allowed during the trial to control blast counts/WBC if the patient is felt to derive benefit from study treatment.
- 9.5 Patients on metformin should be closely watched for elevated metformin levels that could put them at risk for hypoglycemia.

10.0 Adverse Event (AE) Reporting and Monitoring

10.1 Adverse Event Characteristics

CTCAE term (AE description) and grade: The descriptions and grading scales found in the revised NCI Common Terminology Criteria for Adverse Events (CTCAE) version 4.0 will be utilized for AE reporting. All appropriate treatment areas should have access to a copy of the CTCAE version 4.0. A copy of the CTCAE version 4.0 can be downloaded from the CTEP web site: (http://ctep.cancer.gov/protocolDevelopment/electronic_applications/ctc.htm)

- 10.11 Adverse event monitoring and reporting is a routine part of every clinical trial. First, identify and grade the severity of the event using the CTCAE version 4.0. Next, determine whether the event is expected or unexpected (see Section 10.2) and if the adverse event is related to the medical treatment or procedure (see Section 10.3). With this information, determine whether the event must be reported as an expedited report (see Section 10.4). Expedited reports are to be completed within the timeframes and via the mechanisms specified in Section 10.4. All AEs reported via expedited mechanisms must also be reported via the routine data reporting mechanisms defined by the protocol (see Sections 10.6 and 18.0).
- 10.12 Each CTCAE term in the current version is a unique representation of a specific event used for medical documentation and scientific analysis and is a single MedDRA Lowest Level Term (LLT). Grade is an essential element of the Guidelines and, in general, relates to **severity** for the purposes of regulatory reporting to NCI.

NOTE: A severe AE, as defined by the above grading scale, is **NOT** the same as serious AE which is defined in the table in Section 10.4.

- 10.13 Medical conditions/diseases present before starting study treatment are only considered adverse events if they worsen after starting study treatment (any procedures specified in the protocol). Adverse events occurring before starting study treatment but after signing the informed consent form are not recorded. Abnormal laboratory values or test results constitute adverse events only if they induce clinical signs or symptoms or require therapy, and are recorded.
- 10.14 Any serious adverse event occurring after the patient has provided informed consent, has started taking the study medication, and until 4 weeks after the patient has stopped study participation must be reported. This includes the period in which the study protocol interferes with the standard medical treatment given to a patient (e.g. treatment withdrawal during washout period, change in treatment to a fixed dose of concomitant medication). The period after discontinuing study drug may be extended if there is a strong suspicion that the

drug has not yet been eliminated.

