7.4 Toxicity Assessment for Safety Portion (first 6 patients on each Arm)

Toxicity will be measured per NCI-CTCAE version 4. DLT is defined as an adverse event occurring during the first cycle of treatment that is not clearly related to the patient's underlying disease and that meets one of the following:

- Grade 3 AST, ALT or alkaline phosphatase will be considered dose limiting on an individual basis or if lasts more than 5 days
- Grade 3 as per NCI Common Terminology Criteria for Adverse Events (CTCAE) version 4.0 that does not resolve to ≤ Grade 2 within 7 days
- Grade 4 as per NCI Common Terminology Criteria for Adverse Events (CTCAE) version 4.0

NOTE: Myelosuppression will not be considered in evaluating toxicity in patients with acute leukemias or similar advanced myeloid malignancies

(MDS) except where bone marrow (BM) hypoplasia occurs for >52 days with BM cellularity <5% in the absence of residual leukemia/disease.

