7.7 MTD Determination

This MTD determination applies to the Safety Portion. MTD for the safety portion will be defined as the dose level below the lowest dose that induces dose-limiting toxicity in at least one-third of patients (at least 2 of a maximum of 6 new patients).

- 7.71 Three patients will be treated at a given dose level combination and observed for one cycle to assess toxicity (accrual will be suspended while the 3 patients are treated and observed).
- 7.72 If DLT is not seen in any of the 3 patients or in 1 of 3 patients, 3 new patients will be accrued. and treated at the same dose level (accrual will be suspended while the 3 patients are treated and observed). If DLT is seen in 2 or 3 of 3 patients treated at a given dose level, then the next 3 patients will be treated at the next lower dose level, if only 3 patients were enrolled and treated at this lower dose level.
- 7.73After enrolling 6 patients on a specific dose level, if DLT is observed in 1 or less patients, then the combination dose will be considered safe for the expansion phase. If DLT is observed in at least 2 of 6 patients, then the MTD will have been exceeded and defined as the previous dose unless only 3 patients were treated at the lower dose level. In that case, 3 additional patients will be treated at this lower dose level.
- 7.75 If a patient fails to complete one cycle of treatment for reasons other than doselimiting toxicity defined adverse events, the patient will be regarded as noninformative for estimating the MTD and an additional patient will be treated at the current dose level.
- 7.8 Dose escalation will not be allowed for a patient.

7.9a For this protocol, the patient must return to the consenting institution for evaluation at least once every 28 days.

7.9b Local Medical Doctor (LMD) When it has been determined that a patient's malignant disease is stable or objective tumor regression has been observed and the patient is tolerating therapy without excessive toxicity, the drug(s) may be administered by the patient's Local Medical Doctor (LMD). The registering physician retains responsibility for the patient.

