16.4 Secondary Endpoints

- 16.41 Safety and tolerability data will be compiled. The maximum grade for each type of adverse event will be recorded for each patient, and frequency tables will be reviewed to determine patterns (by arm, disease and overall). Additionally, the relationship of the adverse event(s) to the study treatment will be taken into consideration. The rate of grade 3 or higher non-hematologic adverse events, and the rate of grade 4 or higher adverse event (hematologic and non-hematologic) will be computed each with a 95% exact binomial confidence interval.
- 16.42 Summary statistics for clinical benefit (mean and standard deviations for continuous variables and frequencies and percentages for discrete variables) will be compiled for hematologic improvements and transfusion requirements.

- 16.43 Duration of response is defined for all evaluable patients who have achieved a response as the date at which the patient's earliest best objective status is first noted to be a CR/CRi response to the earliest date progression is documented. If a patient dies subsequent to the response without a documentation of disease progression, the patient will be censored at the last date disease was assessed. In the case of a patient failing to return for evaluations before a documentation of disease progression, the patient will be censored for progression on the date of last evaluation. The distribution of duration of response will be estimated using the method of Kaplan-Meier (1958).
- 16.44 Time to response/progression is defined as the time from registration to the earliest date of documentation of response/disease progression. If a patient dies without a documentation of disease progression the patient will censored at the last date disease was assessed. In the case of a patient starting treatment and then never returning for any evaluations, the patient will be censored for progression 1 day post-registration. The distribution of time to progression will be estimated using the method of Kaplan-Meier (1958).
- 16.45 Survival time is defined as the time from registration to death due to any cause. The distribution of survival time will be estimated using the method of Kaplan-Meier (1958).
- 16.46 Time to AML or death is defined for all evaluable patients with MDS as the time from registration to leukemic transformation or death due to any cause. The distribution of time to AML or death will be estimated using the method of Kaplan-Meier (1958).

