16.7 Early Safety Analysis

An early safety analysis will be performed after 6 patients have been accrued to each arm of the study and observed for one cycle. Accrual will be temporarily halted while these patients are evaluated. If 2 or more of the first 6 patients experience a DLT, as defined below, then the dose level will be reduced as defined in Section 8.0 and another six patients will be treated. If < 2/6 patients experience toxicities defined as DLT, then this dose level will be defined as the operational MTD and moved into the expansion portion. Further dose de-escalation to dose level -2 will follow the same guidelines.

Should additional modification be necessary, the study will be closed and evaluated by the study team regarding continuation. Upon determination of the safe dose level, the study will re-open for accrual.

16.8 Data & Safety Monitoring:

- 16.81 The principle investigator(s) and the study statistician will review the study at least twice a year to identify accrual, adverse event, and any endpoint problems that might be developing. The Mayo Clinic Cancer Center (MCCC) Data Safety Monitoring Board (DSMB) is responsible for reviewing accrual and safety data for this trial at least twice a year, based on reports provided by the MCCC Statistical Office.
- 16.82 Adverse Event Stopping Rules: To be evaluated in each arm independently, the stopping rules specified below are based on the knowledge available at study development. We note that the Adverse Event Stopping Rule may be adjusted in the event of either (1) the study re-opening to accrual or (2) at any time during the conduct of the trial and in consideration of newly acquired information regarding the adverse event profile of the treatment(s) under investigation. The study team may choose to suspend accrual because of unexpected adverse event profiles that have not crossed the specified rule below.

Accrual will be temporarily suspended to this study if at any time we observe events considered at least possibly related to study treatment (i.e. an adverse event with attribute specified as "possible," "probable," or "definite") that satisfy one of the following:

- if 3 or more patients in the first 10 treated patients in each arm experience a grade 4 or higher non-hematologic adverse event at least possibly related to treatment.

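### Section 10.13's symptom-or-therapy condition conflicts with the DLT, stopping-rule and adverse event rate definitions, so some severe chemistry abnormalities could go uncounted

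*Combined protocol and SAP*

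**What the plan says.** **The filter.** Section 10.13 limits what may be called an adverse event: "Abnormal laboratory values or test results constitute adverse events only if they induce clinical signs or symptoms or require therapy". Severity grade plays no part.

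**What is built on the filtered term.**
- Section 7.4: "DLT is defined as an adverse event occurring during the first cycle of treatment", after which grade criteria apply.
- Section 10.61: Grade 3 and 4 events outside the solicited list go on the case report form if they are adverse events.
- Section 16.41: rates of Grade 3 or higher non-hematologic events, and "the rate of grade 4 or higher adverse event (hematologic and non-hematologic) will be computed", each with an exact 95% interval.
- Section 16.82: accrual to an arm is suspended if 3 or more of its first 10 patients "experience a grade 4 or higher non-hematologic adverse event" at least possibly related to treatment, or if 30% do so after the first 10.

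**What treats laboratory values as adverse events without the filter.**
- Section 7.4: "Grade 3 AST, ALT or alkaline phosphatase will be considered dose limiting on an individual basis or if lasts more than 5 days".
- Table 8.3: creatinine, bilirubin and ALT/AST increases stand in the adverse event column by CTCAE grade, with no reference to symptoms or therapy.
- The paragraph after that table counts abnormal laboratory values among the adverse events that can interrupt treatment.
- Section 10.6: AST, ALT, neutrophils, platelets and anemia are graded at every evaluation. Bilirubin, creatinine, alkaline phosphatase and electrolytes are not on that list.

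**The concern.** The same laboratory result can be an adverse event under one section and not under another, and no order of precedence is given. A Grade 4 bilirubin rise without symptoms or treatment can trigger a dose action under Table 8.3, yet under 10.13 it need not enter the DLT count, the stopping boundary or the reported rates. Whether withholding study drug counts as therapy for 10.13 is also unstated, so two sites could reasonably code the same event differently.

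The decision rules rest on very few patients. An arm observed at exactly 2 of 6 or 3 of 10 drops below its threshold if one patient is not counted. The affected kind of toxicity is relevant to this drug. Section 1.41 reports dose-limiting toxicities related to serum chemistry with single-dose carboplatin, hyponatraemia as a dose-limiting toxicity with 5-FU, and raised creatinine and hyperbilirubinaemia among related serious events.

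**Working it through.** **1. Which terms are exposed.** Suppose an abnormality is asymptomatic and untreated, so that 10.13 read literally excludes it.

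| Laboratory term | DLT (7.4) | Stopping rule (16.82) | Rates (16.41) |
|---|---|---|---|
| Bilirubin, creatinine, electrolytes | exposed | exposed at Grade 4 | exposed |
| Alkaline phosphatase | named in 7.4 | exposed at Grade 4 | exposed |
| AST, ALT | named in 7.4 | solicited in 10.6 | solicited in 10.6 |
| Neutrophils, platelets, anemia | myelosuppression mostly excluded by 7.4 | non-hematologic events only | solicited in 10.6 |

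**2. Figures in the plan.** The plan gives no operating characteristics for the DLT rule or the stopping rule, so there is nothing to reproduce. Its thresholds are consistent: 2/6 is one-third (7.7) and 3/10 is 30% (16.82). As a check on the binomial calculation, the printed efficacy tables do reproduce:
- Arm A (6 or more of 21): 0.083, 0.231, 0.433, 0.637, 0.799, 0.904.
- Arms B and C (3 or more of 20): 0.075, 0.323, 0.595, 0.794, 0.909.

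**3. Illustration of size.** Let p be the true proportion of patients with a qualifying event. Let f be the share of those patients whose only qualifying event is an uncounted laboratory abnormality. Neither is in the documents; both are assumptions. The counted rate is q = p(1 − f).

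*DLT rule*, with the trigger in 16.7 ("If 2 or more of the first 6 patients experience a DLT"). The 3-then-3 sequence in 7.7 gives the same probability, since 2 of the first 3 already implies at least 2 of 6.

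P(X ≥ 2 of 6) = 1 − (1 − q)^6 − 6q(1 − q)^5, with p = 1/3:
- f = 0, q = 0.333: 1 − 0.0878 − 0.2634 = 0.649
- f = 10%, q = 0.300: 1 − 0.1176 − 0.3025 = 0.580
- f = 25%, q = 0.250: 1 − 0.1780 − 0.3560 = 0.466

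*Stopping rule*, first 10 patients.

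P(X ≥ 3 of 10) = 1 − (1 − q)^10 − 10q(1 − q)^9 − 45q²(1 − q)^8, with p = 0.30:
- f = 0, q = 0.300: 0.617
- f = 10%, q = 0.270: 0.534
- f = 25%, q = 0.225: 0.398

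At f = 10% the loss is 0.07 for the DLT rule and 0.08 for the stopping rule. At f = 25% it is 0.18 and 0.22.

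**The case against.** The strongest reply is that the protocol plainly intends graded chemistry to count: 7.4 and Table 8.3 use laboratory grades without condition, and a specific DLT clause would normally override a general reporting convention. That is persuasive for AST, ALT and alkaline phosphatase in the DLT count, and 10.6 protects AST, ALT and blood counts elsewhere. A reader might infer from 10.13 that no asymptomatic laboratory change can ever be a DLT. The documents do not support that; they contradict themselves rather than exclude such changes uniformly. Abnormalities that require therapy also still count.

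A reader might also assume that half of all qualifying events are silent laboratory findings and so halve the rate, which would take the 3-of-10 probability at a true 30% down to 0.18. That share has no source, and it confuses events with patients, because a patient with any other qualifying event is still counted. With two qualifying events per patient, each independently uncounted half the time, 0.5 × 0.5 = 25% of patients would be lost, not 50%.

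There are other safeguards. The chemistry panel is on the visit schedule, 16.82 lets the team suspend accrual for unexpected adverse event profiles before the boundary is crossed, and the DSMB reviews safety at least twice a year. Registering membership is a stratification factor (6.39d1), so differences in site coding should be roughly balanced between Arms B and C; bias between those arms is not shown. Because the Grade 4 or higher rate includes solicited hematologic events, any understatement would fall mainly on the non-hematologic Grade 3 or higher rate.

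These points narrow the issue but do not close it. Nothing in 7.4 or 10.6 names bilirubin, creatinine or electrolytes, Table 8.3 governs dosing rather than counting, and discretionary review does not replace a defined count.

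**Conclusion.** The inconsistency is real and should be corrected, within limits. It concerns Grade 3-4 bilirubin, creatinine and electrolyte changes that are both asymptomatic and untreated. These are exposed in the DLT count and the 16.41 rates, and at Grade 4 in the 16.82 boundary. Alkaline phosphatase is exposed in the boundary and rates only. Where sites follow 10.13 literally, the error runs one way: triggers fire less often and reported rates are too low.

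The size cannot be derived from the documents. The calculated falls rest on assumed true rates and assumed patient shares of 10% and 25%. They show that the rules are sensitive to the definition, and they do not predict how many events would be missed.

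**What to change.** Reconcile 10.13 with 7.4, 8.3, 10.6, 16.41 and 16.82. State in 10.13 that its symptom-or-therapy condition does not apply when events are counted for 7.4, 16.41 and 16.82. CTCAE-graded laboratory abnormalities that meet the grade criteria already written in those sections would then be recorded and counted. Cross-refer to this from the three sections, and list explicitly any laboratory terms the sponsor means to leave out. This settles which existing text governs counting; it adds no new dose-limiting criterion and changes no treatment rule.

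The cost is one or two sentences, slightly more adverse event entry from chemistry results already collected under Tables 4.1 and 4.2, and somewhat higher reported rates.
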